3.2. Endpoints

The primary safety endpoints are as follows:

1. Occurrence of vaccine-related serious adverse events (SAEs) from the time of first vaccination through the entire study period.
2. Occurrence of severe local and/or systemic solicited reactogenicity signs and symptoms in the 8 days (Day 0-7) after each vaccination.
3. Occurrence of clinical safety laboratory adverse events (AEs) assessed at baseline and 1 month following each vaccination.

The occurrence of these safety parameters will be assessed by treatment group (vaccine and placebo).

The primary efficacy endpoint is:

1. Chronic HCV infection at 6 months defined by persistent viremia over a period of 6 months after detection of incident infection.

The secondary immunogenicity endpoint is:

1. The frequency of positive cell mediated immune response within 14 days after the last vaccination by treatment group (vaccine vs. placebo)

The exploratory efficacy endpoints are as follows:

1. An incident HCV infection will be defined as a new confirmed positive HCV RNA test after a previous negative HCV RNA test. The interval during which incident HCV infection occurs will be defined by the date of the last documented negative HCV RNA results, and the date of the first positive HCV RNA result.
2. Chronic HCV infection at 9 months defined by persistent viremia over a period of 9 months after detection of incident infection.
3. Quantitative viremia measures, including the incident peak and total HCV RNA levels detected, from the date of first HCV RNA detection and at study visits in the first 6 months of viremia will be compared, between vaccinated and placebo groups, using logarithmic IU/mL values.
4. The duration of incident infection will be defined as the interval between incident HCV infection and viral clearance. For subjects who do not clear HCV viremia, the duration will be measured as six months following incident infection. The interval during which incident HCV infection occurs will be defined by the date of the last documented HCV RNA negative results, and the date of the first positive HCV RNA result. The interval during which viral clearance occurs will be defined by the date of the last test with detectable HCV RNA and the first of two consecutive samples with undetectable HCV RNA.

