3.3.5. Duration of Incident Infection

The duration of incident infection will be defined as the midpoint of the interval between incident HCV infection and viral clearance. The incident HCV infection date will be defined as the midpoint of the interval between the date of the last documented HCV RNA negative result and the date of the first positive HCV RNA result. The viral clearance date will be defined as the midpoint of the interval between the date of the

last test with detectable HCV RNA and the first of two consecutive samples with undetectable HCV RNA. For subjects who do not clear HCV viremia, the duration will be measured as six months following incident infection for the fourth exploratory endpoint.

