8.1. Primary Efficacy Analysis

For the evaluation of the primary efficacy objective of this study, a time to event analysis will be performed in the ATP cohort as follows:

- For subjects without HCV infection, the 6-month chronic infection endpoint will be coded as censored, with time to event defined as the elapsed time from the second vaccination, to the end of the 26 months follow up, or to the last observed visit before loss to follow-up or to the earliest time any criterion listed under the censoring criteria for the ATP cohort was met.
- For subjects who develop HCV infection, the 6-month chronic infection endpoint will be coded as an observed event if the 6-month chronic infection endpoint definition is met, and as censored otherwise, with time to event (chronic or non-chronic infection) defined as the elapsed time from the second vaccination to the date of the sample collection with available test result nearest to the target assessment date of six months after incident infection.

Kaplan-Meier curves for chronic HCV infection will be generated for both the ATP and mITT populations (Figure 3 and Figure 4).

As the primary analysis of the primary outcome measure, the reduction in chronic HCV incidence will be calculated from the hazard ratio of a stratified Cox model for the ATP population. The stratification factors that will be used are gender and IL28B status (i.e. there will be four strata: Female & CC, Female & CT/TT, Male & CC, Male & CT/TT). The model to be fit for subject i is:

$$\log h_i(t) = \alpha_j(t) + \beta x_i$$

where $h(t)$ is the hazard function at time t , $\alpha_j(t)$ is the logarithm of the baseline hazard function for strata j , x_i is a binary indicator for membership in the vaccine as compared to the placebo group.

The model described above will be fit and estimates of vaccine efficacy ($1 - \text{Hazard Ratio}$) will be obtained using PROC PHREG following the pseudocode below:

```
proc phreg data=dataset;
model time*status(0) = treatment;
strata gender il28status;
Ods output parameterestimates=ests(keep=HazardRatio HRUpperCL HRLowerCL);
run;
```

Vaccine Efficacy = $1 - \text{Hazardratio}$;

Lower 95% CI = $1 - \text{HRUpperCL}$ which is the same as $1 - \exp(\text{estimate} + \Phi^{-1}(.975) * \text{stderrratio})$

Upper 95% CI= 1 – HRLowerCL which is the same as $1 - \exp(\text{estimate} - \Phi^{-1}(.975) * \text{stderrratio})$

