Analyses will be performed in both ATP and mITT populations. The number of incident HCV infections per treatment group and the vaccine efficacy and associated 95% confidence interval will be summarized by treatment group in [Table 10](#).

For both the standard and interval-censored versions of the Cox model, an additional sensitivity analysis will be performed in which the Cox model will be fit with binary indicators for membership in the vaccine as compared to the placebo group, female as compared to male, and CC IL28B status compared to CT/TT. The interaction between time and gender will be assessed using the product of time and the binary indicator for gender as an interaction term in the model. Likewise, the interaction between time and IL28B status will be assessed using the product of time and the binary indicator for gender as an interaction term in the model. The reduction in incident HCV incidence will be calculated from the hazard ratio of this model.

The model described above will be fit using PROC PHREG following the pseudocode below:

```
proc phreg data=dataset;
model time*status(0) = treatment gender|time il28bstatus|time;
Ods output parameterestimates=ests(keep=HazardRatio HRUpperCL HRLowerCL);
run;
```

```
proc icphreg data=dataset;
    class treatment;
model (StartInterval, EndInterval) = treatment gender|time
il28bstatus|time;
Ods output parameterestimates=ests(keep=HazardRatio HRUpperCL HRLowerCL);
run;
```

These additional sensitivity analyses will be performed in both ATP and mITT populations. Summaries will be provided in [Table 11](#).

The above analyses will be repeated using the secondary definition of incident HCV infection (See Section 3.3.3). The summaries will be presented in [Table 12](#) and [Table 13](#).

Exploratory Objective 2: To determine if AdCh3NSmut1 and MVA-NSmut HCV vaccines will reduce 9-month incidence of chronic HCV infection compared to placebo among HCV-uninfected IDU.

The analysis of this objective will follow exactly the analyses described in Section 8.1 with the following modification:

- For subjects in the ATP (mITT) cohort without HCV infection, the 9-month chronic infection endpoint will be coded as censored, with time to event defined as the elapsed time from the second (first) vaccination, to the end of 26 month follow up, or to the last observed visit before loss to follow-up or of a criterion listed under the censoring criteria for the ATP (mITT) cohort.

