The duration of incident infection (time to spontaneous resolution) is expected to decrease 4-fold in vaccinated subjects who develop viremia (similar to that observed in subjects with HCV reinfection), compared to the placebo group, after 6 months of observation following incident infection. The midpoint between infection and clearance dates will be used to determine duration as previously described (Section 3.3.5). For subjects without observed clearance, the resolution endpoint will be coded as censored, with time to event defined as the elapsed time from the incident infection, to the end of the 6 month follow up, or to the last observed visit before loss to follow-up or to the earliest time any criterion listed under the censoring criteria for the ATP (or mITT) cohort was met.

Analyses of this objective will follow the proportional hazards analysis plan for the primary outcome. Kaplan-Meier curves will be presented in [Figure 9](#) and [Figure 10](#). Regression model summaries will be presented in [Table 22](#) and [Table 23](#). Summary statistics of duration will be presented in [Table 24](#).

Exploratory Objective 5: To determine if AdCh3NSmut1 and MVA-NSmut HCV vaccines will reduce incidence of chronic HCV infection with genotype 1 compared to non-genotype 1 among HCV-uninfected IDU.

A chronic HCV infection genotype 1 will be defined as a chronic HCV infection at 6 months, as defined in Section 3.3.2, with the additional requirement that the infection is genotype 1 as determined from blood samples obtained at the first HCV viremic visit, provided sufficient sample is available.

Because the vaccine is developed from HCV genotype 1b sequences, we hypothesize that we may see greater reduction in chronic infection with HCV genotype 1, compared to other genotypes as a result of stronger genotype specific immune responses: 75% reduction in chronic infection with genotype 1 compared to 45% reduction in chronic infection with non-1 genotypes. These exploratory analyses will be based on estimates of the incidence of HCV genotype 1 infection and non-1 genotypes in each study group using methods for censored survival regression with competing risks (Fine-Gray proportional hazards).

Analyses of this objective will follow the Fine-Gray proportional hazards analysis plan for the Primary Efficacy Objective where two separate models will be fit:

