n = number of HCV-infected subjects with HCV RNA data available after incident infection in the analysis population.
P-value = p-value from two-sided t-test

Tables with similar format:

Table 21: Geometric Mean (GM) Peak HCV RNA Concentrations with 95% Confidence Intervals by Treatment Group— mITT Population

Table 22: Vaccine Efficacy Against Duration of Incident HCV Infection by Treatment Group and Analysis Population

Analysis	Analysis Population	Number of Incident HCV Infections		Vaccine Efficacy [1]	95 % CI for Vaccine Efficacy [2]	P-value [3]
		Vaccine (N=X)	Placebo (N=X)			
Primary Efficacy Analysis	ATP population	x	x	x.xx	x.xx, x.xx	0.xxx
Secondary Efficacy Analysis	mITT population	x	x	x.xx	x.xx, x.xx	0.xxx

Notes: N = Number of subjects in specific treatment group.
 [1] Vaccine efficacy is obtained from stratified Cox regression.
 [2] 95% CI = 95% confidence interval obtained from stratified Cox regression.
 [3] P-value = p-value from score test comparing treatment groups obtained from stratified Cox regression (log-rank test).

Table 23: Stratum-Specific Vaccine Efficacy Against Duration of Incident HCV Infection by Treatment Group and Analysis Population

Analysis		Number of Incident HCV Infections		Vaccine Efficacy [1]	95 % CI for Vaccine Efficacy [2]	P-value [3]
		Vaccine (N=X)	Placebo (N=X)			
ATP Population	All subjects	x	x	x.xx	x.xx, x.xx	0.xxx
	Males	x	x	x.xx	x.xx, x.xx	0.xxx
	Females	x	x	x.xx	x.xx, x.xx	0.xxx
	CC	x	x	x.xx	x.xx, x.xx	0.xxx
	CT/TT	x	x	x.xx	x.xx, x.xx	0.xxx
mITT Population	All subjects	x	x	x.xx	x.xx, x.xx	0.xxx
	Males	x	x	x.xx	x.xx, x.xx	0.xxx
	Females	x	x	x.xx	x.xx, x.xx	0.xxx
	CC	x	x	x.xx	x.xx, x.xx	0.xxx
	CT/TT	x	x	x.xx	x.xx, x.xx	0.xxx

Note: N = Number of subjects in specific treatment group.
 [1] Vaccine efficacy is obtained from stratified Cox regression.
 [2] 95% CI = 95% confidence interval obtained from stratified Cox regression.
 [3] P-value = p-value from score test comparing treatment groups obtained from stratified Cox regression.

Table 24: Summary Statistics of Duration of Incident HCV Infection by Treatment Group and Analysis Population

Statistic	ATP Population		mITT Population	
	Vaccine (N=X)	Placebo (N=X)	Vaccine (N=X)	Placebo (N=X)
Mean	x.x	x.x	x.x	x.x
Standard Deviation	x.x	x.x	x.x	x.x
Median	x.x	x.x	x.x	x.x
Minimum	x	x	x	x
Maximum	x	x	x	x

Table 25: Vaccine Efficacy Against 6-Month Chronic HCV Genotype 1 Infection by Treatment Group and Analysis Population

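### SAP Exploratory Objective 4 applies vaccine efficacy = 1 − HR to viral clearance, a favourable event, so faster clearance would be reported as negative efficacy in Tables 22–23

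*SAP*

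**What the plan says.** The aim in SAP 3.1 and 8.3 is a shorter time to spontaneous resolution in the vaccine arm, and section 8.3 expects a 4-fold decrease in duration. The coding rule makes resolution the event: "For subjects without observed clearance, the resolution endpoint will be coded as censored". Time runs from incident infection and stops at 6 months, at loss to follow-up, or at a cohort censoring criterion.

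For the model and the reported quantity, section 8.3 gives one sentence: "Analyses of this objective will follow the proportional hazards analysis plan for the primary outcome".

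The primary plan is in SAP 8.1. It fits a stratified Cox model with an indicator for vaccine relative to placebo. It continues "The model described above will be fit and estimates of vaccine efficacy", defined there as one minus the hazard ratio, and sets the limits the same way ("Upper 95% CI= 1 – HRLowerCL which is the same as" the exponential form that follows). The definition recurs for Objective 1 in section 8.3. The SAP gives no other definition of vaccine efficacy.

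The shell in SAP Appendix 1 is headed "Table 22: Vaccine Efficacy Against Duration of Incident HCV Infection by Treatment Group and Analysis Population", and Table 23 is its stratum-specific counterpart. Both have a vaccine efficacy column with a 95% CI, footnoted as coming from stratified Cox regression, and both give the number of incident infections per arm.

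**The concern.** One minus the hazard ratio reads as efficacy only when the event is something the vaccine should prevent. In Objective 4 the event is something the vaccine should bring forward, so a benefit is HR > 1 and the formula returns a negative number.

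Negative efficacy means harm in Table 8 and the other efficacy tables. In Tables 22–23 the same label would mean benefit, with no warning to the reader. The prespecified hypothesis, if true, would appear as an adverse result, and a vaccine that delayed clearance would appear efficacious. The same report would also contain Kaplan–Meier curves (Figures 9–10) and duration summaries (Table 24) pointing the other way.

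**Working it through.** **The convention on the primary endpoint.** SAP section 5 assumes 14 and 5.6 chronic infections per 100 person-years. HR = 5.6/14 = 0.40, so efficacy = 1 − 0.40 = +60%. The stated 43 events reproduce from Schoenfeld's formula: 4 × (1.960 + 1.036)² / (ln 0.40)² = 42.8, rounded up to 43. The event is harmful, and a positive value means benefit. The documents give no hazard ratio, event count or power for Objective 4.

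**The sign for Objective 4.** The event is clearance and the indicator is vaccine versus placebo. Faster clearance means HR > 1, so 1 − HR < 0. Slower clearance means HR < 1, so 1 − HR > 0. For example, HR 0.5 gives +50%, HR 1.5 gives −50% and HR 2 gives −100%. No distributional assumption is needed for the sign.

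**The size under the SAP's expected 4-fold effect (SAP 8.3).** Two readings:

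- *All clearance times exponential.* A mean duration one quarter as long gives HR = 4 and 1 − 4 = −300%. Simulation with 20,000 per arm, censored at 6 months, and placebo clearance of 20–30% by 6 months gave HR 3.90 to 4.02, that is −290% to −302%.
- *Only some subjects ever clear, and only their speed changes.* Let a fraction c clear in either arm. Clearers are exponential with 86% cleared by 6 months under placebo (Protocol 11.4.5, read as a share of those who clear), so the rate is −ln(0.14)/6 per month; it is 4 times that under vaccine. Solving the large-sample Cox score equation over 6 months gives HR of about 1.25, 1.30 and 1.43 for c = 0.20, 0.30 and 0.48. The table would show about −25%, −30% and −43%.

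**The size if the primary hypothesis worked only through clearance.** Assume no effect on acquisition and proportional clearance hazards over 6 months. With placebo persistence p and vaccine persistence 0.4p, the clearance HR is ln(0.4p)/ln(p).

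| Placebo persistence p | Source | 0.4p | Clearance HR | 1 − HR |
|---|---|---|---|---|
| 14/27 = 0.519 | Protocol 11.2 and 11.4.5 rates | 0.207 | 2.40 | −140% |
| 0.70 | Protocol 2.1 | 0.280 | 3.57 | −257% |
| 0.80 | Protocol 2.1 | 0.320 | 5.11 | −411% |

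In each row Table 8 would show +60% while Table 22 showed the last column, from the same vaccine effect.

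**The confidence limits.** Take the first row with about 146.25 × 1.5 × 0.27 = 59 infections per arm (depletion ignored). Clearances are 59.2 × 0.481 = 28.5 and 59.2 × 0.793 = 46.9, and SE(ln HR) is about √(1/28.5 + 1/46.9) = 0.237. HR 2.40 (1.50 to 3.81) becomes −140% (−281% to −50%). The limits are in the correct order for 1 − HR, so the limit formulas are not at fault; only the meaning of the sign is reversed.

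**The case against.** - *Objective 4 does not adopt the primary plan unchanged.* Section 8.3 gives it its own event, time origin and horizon. This is correct, and it weakens any contrast with Objective 2, where the SAP says "The analysis of this objective will follow exactly the analyses described in Section 8.1 with the following modification". The narrower statement stands: no change to the effect measure is given.
- *The table footnotes do not print 1 − HR.* They say only that efficacy comes from stratified Cox regression, so the fault is inferred from a cross-reference and a column label. But 1 − HR is the SAP's only definition of vaccine efficacy, and a programmer following the text has no other formula to use.
- *The illustrated sizes come mostly from assumptions outside the plan.* They run from about −25% to −411%. The ratio 14/27 divides a design assumption by a separately quoted infection rate and sits below the 70–80% chronicity in Protocol 2.1. The clearance-only scenario also ignores any effect on acquisition, which Objective 1 tests. This is fair: the figures only illustrate, and the sign alone carries the point.
- *Infections are a natural at-risk count.* They are, so the existing column in Tables 22–23 is not itself an error. The number of modelled events is still missing.
- *Little depends on it.* The endpoint is exploratory, the two-sided score test is unaffected by the sign, and a large negative efficacy beside shorter durations in Table 24 would be noticed. This limits the priority but does not remove the contradiction within the report.

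**Conclusion.** The concern holds. Followed as written, the SAP would report faster clearance as negative vaccine efficacy and slower clearance as positive. This rests only on the event coding in section 8.3, the formula in section 8.1 and the column in Tables 22–23. The size cannot be fixed from the documents: it is −300% if the 4-fold effect acts on exponential times in everyone infected, and about −25% to −43% if it acts only on the speed of those who clear.

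This is an effect-measure and labelling error in an exploratory analysis. It does not touch the primary result, the p-values, Figures 9–10 or Table 24. It should be corrected, but nothing confirmatory depends on it.

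**What to change.** In SAP 8.3, Objective 4, state that the reported effect is the hazard ratio for clearance, vaccine versus placebo, with its 95% CI and the score-test p-value; that HR > 1 favours vaccine; and that 1 − HR is not applied. Retitle Tables 22–23, for example as the hazard ratio for clearance of incident HCV infection, and replace the efficacy column. Show the number of clearances beside the number of infections in each arm.

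A minor wording correction can go in with it. SAP 3.2 has "The duration of incident infection will be defined as the interval between incident HCV infection and viral clearance", whereas SAP 3.3.5 has "The duration of incident infection will be defined as the midpoint of the interval between incident HCV infection and viral clearance", and section 8.3 repeats the midpoint wording. Both should state duration as the clearance midpoint date minus the infection midpoint date. The intent can be recovered from the date definitions in 3.3.5, so this is tidying only. The 6-month censoring rule in section 8.3 needs no change.

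The cost is SAP text and table-shell edits. No new data, model or sample size is needed.

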7.6.2 Endpoint Assays: HCV serology and virology

HCV RNA

HCV RNA will be monitored using both qualitative and quantitative assays.

Qualitative HCV RNA testing:

A standardized HCV RNA qualitative assay (Procleix[®] HIV-1/HCV assay, by Gen-Probe Inc., San Diego, CA) with 50% limit of detection of 12.1 copies/mL of HCV RNA when using the recommended 0.5 mL specimen input (95% CI, 11.1 to 13.2) will be used to screen for HCV RNA at monitoring visits. HCV reactive samples will be confirmed using a quantitative HCV RNA assay based on real-time PCR (Procleix HCV assay; Gene-Probe). (This assay will not be used for HIV screening).

Quantitative HCV RNA testing:

Quantitative HCV RNA testing (based on real-time PCR (Procleix HCV assay; Gene-Probe) will be used to confirm HCV infection. Monitoring of HCV infection relies on sensitive and accurate HCV RNA detection by quantitative assays. Recently developed tests based on real time PCR have a high sensitivity (based on the lower limit for detecting HCV RNA) and a great dynamic range. The principle of real-time PCR techniques is to detect amplicon synthesis and to deduce the number of viral genomes in the start of the clinical sample during the PCR rather than at the end. The main advantage of tests based on real time PCR is that each has been standardized, which makes results by different laboratories comparable through reporting in international units (IU).

HCV subtypes

HCV genotype will be determined by reverse transcription/nested PCR (nt 85--1326 core-E1 region amplicon) following nucleic acid extraction on automated instrumentation. Genotype is determined by sequence comparison with GenBank using BLAST. Viral sequencing of HCV Core-E1 sequences of initial infections will be conducted to determine HCV subtype on the first quantitative measurement of HCV RNA, dependent on specimen availability and RNA level. In patients who demonstrate alternating HCV RNA positive and negative results or who have missed more than two follow up study visits, viral sequencing will be used to confirm reinfection with a different virus or intercalating viremia with the same virus.^{29,84}

HCV antibodies

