5. SAMPLE SIZE CONSIDERATIONS

Sample size calculations are based on the assumption of detecting a 60% reduction in incidence of chronic infection over 18 months of post-vaccination follow-up among vaccinated subjects compared to unvaccinated controls in an according to protocol (ATP) analysis. A total of 43 observed events of chronic infection in the ATP cohort would provide power of 85% for a two-sided log rank test conducted at the significance level (alpha) of 0.05 to detect a 60% reduction in hazard rate. The incidence of chronic infection among controls is assumed to be 14% annually [10]. Assuming 14 cases/100 person-years (PY) in the control group, and 5.6 cases/100 PY in the vaccine group, a total of 292.5 subjects in the ATP cohort followed for 1.5 years would provide on average 43 events. We further assume that 65% of enrolled subjects will be retained in the ATP cohort. Therefore, we inflate the required number of subjects by a factor of $1/0.65$ and obtain a target enrollment of 540 subjects, or 270 subjects per vaccination group.

The original enrollment target of the study was 344 subjects. At the April 29, 2014 DSMB meeting, the DSMB reviewed the progress towards the goal of 43 observed events of chronic infection in the ATP cohort and recommended increasing the target enrollment from 344 to 450, or 225 subjects per vaccination group.

At the September 2, 2015 DSMB meeting, the DSMB reviewed the progress towards the goal of 43 observed events of chronic infection in the ATP cohort and recommended increasing the target enrollment from 450 to 540 subjects, or 270 subjects per vaccination group.

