- The primary event of interest is chronic HCV with genotype 1 and the competing event is chronic HCV with genotype other than 1.
- The primary event of interest is chronic HCV with genotype other than 1 and the competing event is chronic HCV with genotype 1.

Kaplan-Meier curves will be presented in [Figure 11](#) and [Figure 12](#). Regression model summaries will be presented in [Table 25](#) and [Table 26](#).

Additional Exploratory Analyses

A summary of study rates by treatment group and site are provided in [Table 27](#) and [Table 28](#), respectively.

With regard to the primary efficacy endpoint, as all possible cases, including cases with uncertain classification for chronicity, will be reviewed by a blinded independent endpoint review committee (ERC) to make a determination of infection outcome. This committee will be comprised of the study PIs, HCV experts, and the SDCC. An interim case review committee comprised of HCV experts, the SDCC, and DMID met on October 14, 2016 and the members were concerned that the endpoint definition in the protocol does not account for subjects with mixed genotype infections; so, if a person's dominant genotype changes over the 6-month period, per the protocol, the subject would not be included as a 6-month chronically infected endpoint case but, in practice, the person still has chronic HCV infection. It was proposed that in addition to the "per protocol" assessments, that the ERC voting members provide their "real-world" and "expert clinical" assessment. The Committee asked that an exploratory analysis of 6-month and 9-month chronicity be conducted using their "expert clinical" non-per protocol assessment of chronic infections to include these more complex cases of potential mixed infections and to include subjects who miss the 6-month visit window, but remain viremic afterwards.

At the final ERC review, the committee will determine case status per protocol as well as ERC-defined cases. The number of 6 and 9 month chronic HCV infections as determined by the ERC per treatment group and the vaccine efficacy and associated 95% confidence interval will be summarized by treatment group in [Table 29](#) and [Table 30](#) for the mITT and ATP populations.

Subject listings of HCV infection status and HCV positive quantitative results are provided in [Listing 24](#) and [Listing 25](#), respectively. A listing of genotyping results, sequence evaluation and ERC Assessment is provided in [Listing 26](#).

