Analysis	Analysis Population	Number of Chronic HCV Infections		Vaccine Efficacy [1]	95 % CI for Vaccine Efficacy [2]	P-value [3]
		Vaccine (N=X)	Placebo (N=X)			
Primary Efficacy Analysis	ATP population	x	x	x.xx	x.xx, x.xx	0.xxx
Secondary Efficacy Analysis	mITT population	x	x	x.xx	x.xx, x.xx	0.xxx

Note: N = Number of subjects in specific treatment group.
 [1] Vaccine efficacy is obtained from Fine-Gray proportional hazards.
 [2] 95% CI = 95% confidence interval obtained from Cox regression.
 [3] P-value = p-value from log-rank test comparing treatment groups obtained from Cox regression.

Tables with similar format:

Table 26: Vaccine Efficacy Against 6-Month Chronic HCV Genotype non-1 Infection by Treatment Group and Analysis Population

Table 27: Summary of Study Rates by Treatment Group- All Enrolled Subjects

Rate	Vaccine (N=X)	Placebo (N=X)	All Subjects (N=X)
Enrollment Rate	xx.x / month	xx.x / month	xx.x / month
Early Discontinuation Rate	xx.x / 100 PYO	xx.x / 100 PYO	xx.x / 100 PYO
Loss from mITT Population Rate	xx.x / 100 PYO	xx.x / 100 PYO	xx.x / 100 PYO
Loss from ATP Population Rate	xx.x / 100 PYO	xx.x / 100 PYO	xx.x / 100 PYO
HCV + Incidence Rate	xx.x / 100 PYO	xx.x / 100 PYO	xx.x / 100 PYO
HCV + Incidence Rate – mITT Population	xx.x / 100 PYO	xx.x / 100 PYO	xx.x / 100 PYO
HCV + Incidence Rate – ATP Population	xx.x / 100 PYO	xx.x / 100 PYO	xx.x / 100 PYO
Chronic HCV + Incidence Rate	xx.x / 100 PYO	xx.x / 100 PYO	xx.x / 100 PYO
Chronic HCV + Incidence Rate – mITT Population	xx.x / 100 PYO	xx.x / 100 PYO	xx.x / 100 PYO
Chronic HCV + Incidence Rate – ATP Population	xx.x / 100 PYO	xx.x / 100 PYO	xx.x / 100 PYO
Chronic HCV + (Genotype 1) Incidence Rate	xx.x / 100 PYO	xx.x / 100 PYO	xx.x / 100 PYO
Chronic HCV + (Genotype 1) Incidence Rate – mITT Population	xx.x / 100 PYO	xx.x / 100 PYO	xx.x / 100 PYO
Chronic HCV + (Genotype 1) Incidence Rate – ATP Population	xx.x / 100 PYO	xx.x / 100 PYO	xx.x / 100 PYO
Chronic HCV + (Genotype non-1) Incidence Rate	xx.x / 100 PYO	xx.x / 100 PYO	xx.x / 100 PYO
Chronic HCV + (Genotype non-1) Incidence Rate – mITT Population	xx.x / 100 PYO	xx.x / 100 PYO	xx.x / 100 PYO
Chronic HCV + (Genotype non-1) Incidence Rate – ATP Population	xx.x / 100 PYO	xx.x / 100 PYO	xx.x / 100 PYO
Note: PYO=Person-years of observation N=Number of subjects enrolled in the respective treatment group			

Table 28: Summary of Study Rates by Site-All Enrolled Subjects

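### Exploratory Objective 5 asks whether the vaccine works better against genotype 1 than non-1, but the SAP plans no estimate of that difference, and the Table 25 footnotes mix Fine-Gray and Cox results

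*SAP*

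**What the plan says.** SAP 8.3 words Exploratory Objective 5 as genotype 1 against non-genotype 1 and gives a hypothesis of "75% reduction in chronic infection with genotype 1 compared to 45% reduction in chronic infection with non-1 genotypes". The method follows: "Analyses of this objective will follow the Fine-Gray proportional hazards analysis plan for the Primary Efficacy Objective where two separate models will be fit". The first model takes chronic genotype 1 infection as the event, with other genotypes competing. The second reverses the roles: "The primary event of interest is chronic HCV with genotype other than 1 and the competing event is chronic HCV with genotype 1".

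Tables 25 and 26 report counts, efficacy, CI and p-value for vaccine against placebo, one class per table. Tables 27 and 28 add genotype-specific rates by arm and by site. Neither document plans a ratio, difference, interaction or test between classes.

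Under Table 25, the efficacy footnote reads "1] Vaccine efficacy is obtained from Fine-Gray proportional hazards" and the interval footnote reads "2] 95% CI = 95% confidence interval obtained from Cox regression". The third footnote takes the p-value from a log-rank test out of Cox regression. Table 26 uses the same format. By contrast, the Fine-Gray code in SAP 8.1, which Objective 5 adopts, outputs the hazard ratio and both limits from one fit.

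**The concern.** Two separate within-class tests do not answer a between-class question. A reader who sees one significant and one non-significant p-value may take that as evidence of genotype-specific protection; two significant results may be taken as evidence of none. Neither inference is sound without an estimate of the difference and its uncertainty.

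The footnotes are a separate fault. A programmer cannot follow both the Table 25 footnotes and the method in SAP 8.3. As footnoted, the efficacy and its interval would come from different models.

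**Working it through.** **Inputs.** SAP section 5 gives 43 events, two-sided alpha 0.05, 85% power, 14 and 5.6 cases per 100 person-years, and the aim of "detecting a 60% reduction in incidence of chronic infection over 18 months of post-vaccination follow-up" (HR 0.40). SAP 8.3 gives HRs of 0.25 and 0.55. No genotype 1 share is stated for the trial population. I assume 50%, because the plan's effects then average to its overall effect: 0.5 × 0.25 + 0.5 × 0.55 = 0.40. No passage makes that derivation, so I also show 30% to 70%, and 88.5%, which protocol 2.1 gives for known US isolates.

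**The plan's own figure.** Schoenfeld: events = 4(1.96 + 1.036)²/(ln 0.40)² = 42.8, so 43. Power at 43 events is 85.2%. This reproduces.

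**Chance of exactly one significant test when efficacy is the same in both classes.** Power per class = Φ(|ln HR|√d/2 − 1.96) plus the opposite tail, with the two tests treated as independent. At an even split d = 21.5, and the chance is 2p(1 − p). The total is held at 43 events.

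| True efficacy, both classes | Power per class, p | Exactly one significant |
|---|---|---|
| 0% | 0.050 | 9.5% |
| 30% | 0.131 | 23% |
| 60% | 0.565 | 49% |
| 80% | 0.962 | 7% |

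At 60% efficacy, other shares give:
- 30% or 70%: 55%.
- 40% or 60%: 51%.
- 88.5%: class powers 0.807 and 0.175, so 0.807 × 0.825 + 0.175 × 0.193 = 70%. In 67% of trials genotype 1 alone would be significant.

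A Poisson simulation at the plan's rates gives 50% at an even split.

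**Precision within a class** (60% efficacy, even split). Placebo events 43/1.4 × 0.5 = 15.36; vaccine events 6.14. SE = √(1/15.36 + 1/6.14) = 0.477. HR 0.40 × exp(±1.96 × 0.477) = 0.157 to 1.020, an efficacy interval of −2% to 84%.

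**The missing contrast under 75% versus 45%.** The variance of the log ratio of HRs is the sum of 1/events over four cells. At a 50% share the cells are 15.4 and 3.8 (genotype 1, placebo and vaccine) and 15.4 and 8.4 (non-1). SE = 0.714. The ratio 0.25/0.55 = 0.45 has a 95% CI of 0.11 to 1.84, a factor of 4.05 each way.

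| Genotype 1 share | Power, normal approximation | Power, simulation | Trials with an empty cell |
|---|---|---|---|
| 30% | 16% | about 5% | 11% |
| 50% | 20% | 14% | 2% |
| 70% | 20% | 18% | 1% |
| 88.5% | 13% | 13% | 14% |

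The simulation draws Poisson cell counts, adds 0.5 to each and applies a Wald test.

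**Size of the footnote mismatch.** Take a placebo hazard of 0.07 per year per class over 1.5 years. Cumulative incidence is 9.47% in each placebo class, and 2.52% (genotype 1) and 5.54% (non-1) on vaccine. The subdistribution HR is ln(1 − CIF vaccine)/ln(1 − CIF placebo): 0.256 and 0.573, against cause-specific 0.25 and 0.55.

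**The case against.** The strongest reply is that class-specific efficacy is all the plan intended. Protocol 11.4.5 describes comparisons between study groups, SAP 8.3 speaks of estimates within each group, and both efficacies are reported with intervals. Protocol 11.1 already warns that the sample will not support definitive conclusions, and nothing in either document says genotype specificity will be judged by comparing p-values. This stands in part: the misreading is a risk, not a stated plan, and the contrast will be imprecise. It does not remove the gap, because the objective and its hypothesis are both worded as a comparison.

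A second reply is that the footnotes are carried-over mock-up wording. That is likely: Cox footnotes also sit under the Fine-Gray rows of Tables 8, 9, 14, 15 and 29. The effect is small, but the text still needs correcting.

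A reader might also infer that missing genotypes could seriously distort this objective, since genotype is "determined from blood samples obtained at the first HCV viremic visit, provided sufficient sample is available" and protocol 7.6.2 makes sequencing "dependent on specimen availability and RNA level". The documents do not support that. SAP 3.3.2 lets a supplemental or first H-series sample identify the incident virus when the first cannot be tested, and Listing 26 has a combined incident/H01 genotype column. No passage gives a rate of ungenotyped cases. How to code any that remain is a minor clarification. So is the form of Figures 11 and 12, which are Kaplan-Meier curves for genotype 1 only.

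**Conclusion.** The point holds as a minor one. The SAP states a comparative exploratory objective and plans no estimate of the comparison, and the Table 25 footnotes contradict the method in SAP 8.3 and the code in SAP 8.1.

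It would be tempting to say that discordant p-values arise in about half of all trials with equal efficacy. That holds only near 60% true efficacy at 43 events. The figure is much lower at zero, 30% or 80% efficacy, and higher if one genotype dominates. The 50% share is assumed, and 88.5% describes known US isolates, not this trial's population.

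Nor do the documents support reading this as a threat to the trial's main result. Objective 5 is exploratory, and the primary Cox analysis does not use genotype class.

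**What to change.** 1. Correct the Table 25 and 26 footnotes so that efficacy, CI and p-value all come from the same Fine-Gray fit. Align the footnotes for the Fine-Gray rows of Tables 8, 9, 14, 15 and 29.
2. Add one stacked cause-specific Cox model: two rows per subject (genotype 1 and non-1), a separate treatment term for each, and strata for gender, IL28B status and genotype class. Report the two cause-specific HRs and their ratio with a 95% CI. Label the ratio descriptive, imprecise and not the ratio of the Fine-Gray efficacies. State that one significant and one non-significant result is not evidence of a difference.
3. Specify a small-sample interval, such as profile likelihood or Firth, for use if an arm-by-genotype cell is empty.

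The cost is one extra model and some footnote edits, with no new data. The downside is one more exploratory estimate with a wide interval. Fixing it before unblinding sets the contrast before anyone knows which class looks better.
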